NAFLD is a growing threat to public health. Nonalcoholic fatty liver disease (NAFLD), which encompasses a spectrum from simple steatosis and steatohepatitis (NASH) to fibrosis and cirrhosis, is the leading cause of liver disease in the United States. The prevalence in U.S. adults is estimated to be 25-30% (1, 2), rising to over 50% among adults with obesity or Type 2 diabetes (T2D) (3-5). Of those with NAFLD, approximately one-fifth have NASH (6). Studies of liver transplantation since the early 2000s demonstrate several-fold increases in transplants performed for NASH (7, 8). In 2013, NASH became the second-leading cause of liver transplant, after hepatitis C (HCV) (9). With new pharmacologic treatments for HCV, NASH will likely overtake HCV as the leading indication for liver transplantation in the next decade (10).

NAFLD is a multisystem disease. NAFLD independently contributes to T2D and cardiovascular disease (CVD) (11). Mechanisms include inflammation and hepatic dysfunction as well as steatosis itself. This is an important point: although simple steatosis is thought to be benign in terms of liver outcomes, it is not metabolically benign. **Diabetes risk:** Multiple studies demonstrate that intrahepatic lipid is independently associated with peripheral insulin sensitivity in humans (12-16), and the presence of fatty liver increases the risk for incident T2D (17, 18). Further, improvements in fatty liver over time reduce diabetes risk, whereas worsening of fatty liver markedly increases the risk of incident T2D (19). Shulman and colleagues have shown that accumulation of diacylglycerol (DAG) in hepatocytes is strongly associated with activation of PKC ϵ , which impairs insulin signaling (20). This putative mechanism by which hepatic lipid induces insulin resistance is independent of inflammation; in fact, DAG content is more strongly predictive of hepatic insulin resistance than are markers of hepatic inflammation (20). **CVD risk:** NAFLD is independently associated with CVD, the leading cause of death in NAFLD. Hepatic steatosis is associated with coronary artery calcification (21) and increased high-risk plaques (22), independent of traditional CVD risk factors and visceral fat content. Further, individuals with NAFLD have more rapid progression of CAC during follow-up compared to controls (23). Among individuals with T2D, NAFLD at baseline conveys an 84% increase in the odds of a CVD event over 5 years, independent of metabolic syndrome features, age, sex, smoking, LDL, and liver enzymes (24).

There is a significant need for highly effective treatments for NAFLD. There are currently no FDA-approved pharmacologic therapies for NAFLD and NASH, and diet and exercise are often minimally effective. Vitamin E improves histology in some patients in randomized trials (25), but concerns remain that it may increase risk of prostate cancer and all-cause mortality (26, 27). Pioglitazone also improves histological features of NASH (25, 28) but causes weight gain and may increase the risk of bladder cancer (28, 29). Both elafibranor (30) and obeticholic acid (31) have improved histological features of NASH, but neither has completed Phase 3 trials. Further, obeticholic acid increases LDL and decreases HDL (31, 32). Thus, continued investigation of strategies to treat NAFLD and NASH is greatly needed. This protocol aims to treat NAFLD and NASH by reversing the physiologic reduction in growth hormone (GH) that occurs in obesity in order to alter hepatic lipid metabolism, reduce liver fat, and ameliorate NASH.

Strong rationale exists for using GH Releasing Hormone (GHRH) to treat NAFLD in obese adults. In obese adults, we and others have demonstrated that increased adiposity, particularly abdominal adiposity, is associated with significant reductions in GH secretion (33-35). There is an inverse association between visceral adipose tissue (VAT) and GH secretion, assessed by peak GH response on provocative testing, in men and women of varying BMIs. Further, obesity-related reductions in GH are strongly associated with dyslipidemia and metabolic abnormalities (34, 36).

Patients with pituitary GH deficiency (GHD) have a high prevalence of NAFLD and NASH (37-40), and GH replacement reduces aminotransaminase levels and improves liver histology (39, 41). Further, individuals with childhood onset GHD in whom GH is stopped at attainment of final height demonstrate a high incidence of NAFLD, developing as soon as 1 year after GH discontinuation (42). Obesity-related reductions in GH also appear to be associated with increased liver fat (43). Among 142 adults who had liver biopsy during NAFLD evaluation or weight loss surgery, mean serum IGF-1 was lower in subjects with lobular inflammation ($p=0.01$), higher fibrosis stage ($p=0.005$), and NASH ($p=0.002$), with all associations persisting after controlling for age, BMI, and presence of diabetes or cirrhosis (44).

Animal models demonstrate a clear role for GH in pathogenesis of NAFLD and NASH. GH signals through STAT5 to exert multiple effects on lipid metabolism, including (1) suppression of hepatic *de novo* lipogenesis (DNL) (48-53), (2) stimulation of lipolysis (54, 55), (3) increased lipid utilization through β -oxidation (56, 57), and (4) suppression of 11 β HSD1 activity, which impacts lipid metabolism by decreasing the conversion of cortisone to active cortisol at a tissue level (58, 59). The physiologic relevance of GH in lipid metabolism is demonstrated in multiple animal models, as shown in **Table 1**. Importantly, lack of GH-signaling in these models is associated not only with simple steatosis, but also with steatohepatitis.

Table 1: Evidence from rodent models linking GH insufficiency to NAFLD and NASH

| |
|---|
| Spontaneous Dwarf Rat (GH gene mutation) (45) |
| 
 steatosis, fibrosis, and hepatocyte injury elevated AST and ALT |
| Liver-specific GH-receptor KO mouse (46, 47): |
| 
 severe hepatic steatosis increased hepatic lipid uptake increased hepatic lipogenesis upregulation of inflammatory cytokines elevated AST and ALT |

GHRH is a safe and effective means to augment endogenous GH secretion. GH is secreted in a pulsatile manner from the pituitary in response to positive stimulation by GHRH, counterbalanced by negative feedback from somatostatin and IGF-1. GHRH is a safe and effective means to increase endogenous GH secretion in individuals with intact pituitary function for two reasons. First, administration of GHRH preserves negative feedback by IGF-1 and somatostatin, thus decreasing the potential for supraphysiologic elevations in IGF-1. Second, GHRH preserves endogenous GH pulsatility. As is the case with multiple other hormones, pulsatile GH signals at a tissue level differently than apulsatile GH (60, 61). For example, two human studies show that pulsatile GH increases lipolysis to a greater degree than apulsatile delivery (62, 63). The study drug, tesamorelin, is a GHRH analog that has been minimally modified with c-terminal amidation to increase half-life. It has been FDA approved since 2010 for reduction of visceral fat in individuals with HIV-lipodystrophy (64-67). We have shown that tesamorelin increases endogenous GH levels by increasing both basal and pulsatile GH secretion (68). A summary of clinical safety data on tesamorelin (GHRH) is shown in **Table 2**.

Table 2: Summary of Clinical Safety Data for GHRH Analog (tesamorelin)

Known side effects: Injection site redness or itching (7-8%), peripheral edema (6%), myalgia (6%) (66)

Effects on glycemia: • Phase 3 studies in HIV: average increase in HbA1c of 0.1% after 6 months, with return to baseline after 12 months; no changes in fasting insulin or glucose (66). • Our research in HIV: increase in fasting glucose by 7mg/dL at 2 weeks and decrease in insulin sensitivity by euglycemic clamp at 3 months, both of which returned to baseline by 6 months of treatment (69). • Adults with T2D: modest initial increases in fasting insulin and glucose, return to baseline at 12 weeks (70)

Serious Adverse Events: Not different from placebo (64-66, 69, 71)

The purpose of this protocol is to test the effects of treatment with a GHRH analogue, tesamorelin (Theratechnologies, Inc.), in individuals with known NAFLD, with the hypotheses that augmentation of endogenous GH secretion will decrease liver fat, improve histologic features steatohepatitis, and improve cardiovascular risk, inflammation, and lipid metabolism.

I. Specific Aims

The Specific Aims will be addressed in a 12-month, randomized, controlled trial of 76 individuals with NAFLD, treated with tesamorelin vs. placebo. A 6-month open-label extension phase will maximize recruitment and retention and provide data regarding longer-term use of tesamorelin.

Specific Aim 1: Tesamorelin will significantly decrease liver fat and improve histologic features of NASH in patients with biopsy-proven NASH. We hypothesize that,

- Tesamorelin will significantly decrease hepatic fat fraction as measured by ^1H -MRS (1° endpoint).
- Tesamorelin will significantly improve liver histology as assessed by increased 1) frequency of ≥ 2 point reduction in NAFLD activity score (NAS) without worsening of fibrosis and 2) reduction in individual components of the NAS including steatosis, lobular inflammation and hepatocyte ballooning.

Specific Aim 2: Tesamorelin will be associated with beneficial changes in hepatic lipid metabolism and

inflammatory milieu.

- a) Tesamorelin will decrease hepatic de novo lipogenesis as measured by stable isotopes.
- b) Hepatic expression of lipogenic genes (SCD1, FAS, SREBP1c) will decrease and expression of lipolytic genes (PPAR α , CPT1) will increase.
- c) Tesamorelin will reduce hepatic expression of pro-inflammatory (MCP1, TNF α , IL-1 β , IL-6, IL-18, TLR, MyD88, CCL5, TGF β 1, NF κ B) and fibrogenic (TIMP1, COL1A1, MMP1-14) genes.

Specific Aim 3: Tesamorelin will reduce markers of cardiometabolic risk in individuals with NASH.

These changes will be associated with reduction in liver fat and liver inflammation.

- a) Tesamorelin will improve circulating lipid (TG, HDL, TC), C-reactive protein, tissue plasminogen activator antigen and plasminogen activator inhibitor-1 antigen and adiponectin levels.

II. Subject Selection

Seventy-six obese men and women ages 18-65yo with either known hepatic steatosis on recent biopsy or with $\geq 5\%$ hepatic fat fraction on ^1H -MRS, will be recruited, with eligibility criteria as below. A threshold of 5% hepatic fat fraction on ^1H -MRS is included because undiagnosed hepatic steatosis is prevalent in obesity, and hepatic fat fraction on MRS correlates extremely well with histological findings (87, 88). Further, a threshold of 5% approximates the 95th percentile of hepatic fat fraction in the normal, healthy population as reported by Szczepaniak et al. (1).

Inclusion criteria

1. Men and women 18-65yo
2. BMI $\geq 25\text{kg}/\text{m}^2$
3. Hepatic steatosis as demonstrated by either a) Grade ≥ 1 steatosis on a liver biopsy performed within 12 months of the baseline visit, without $>10\%$ reduction in body weight or addition of medications to treat fatty liver, or b) liver fat fraction $\geq 5\%$ on ^1H -MRS
4. Hepatitis C antibody and Hepatitis B surface antigen negative. Subjects without known history of Hepatitis C or Hepatitis C treatment who have a positive Hepatitis C antibody but a negative hepatitis C viral load will also be eligible.
5. For females ≥ 50 yo, negative mammogram within 1 year of baseline
6. If use of vitamin E ≥ 400 IU, stable dose for ≥ 6 mos
7. Up to date with colon cancer screening recommended by the participant's primary care physician, using whatever methodology the primary physician recommends. This will be ascertained by self-report. (If a participant does not have a primary care physician, we will discuss that colon cancer screening is recommended, typically starting at age 50y, and refer the participant to primary care through Partners if s/he desires.)

Exclusion criteria

1. Heavy alcohol use defined as consumption of $> 20\text{g}$ daily for women or $> 30\text{mg}$ daily for men for at least 3 consecutive months over the past 5 years assessed using the Lifetime Drinking History Questionnaire (25, 89)
2. Known diagnosis of diabetes, use of any anti-diabetic medications (including thiazolidinediones or metformin), fasting glucose $> 126\text{mg}/\text{dL}$, or HbA1c $\geq 6.5\%$. Participants with stable use of metformin ≥ 6 months will be permitted if it is being used for pre-diabetes or another non-diabetes indication (e.g., PCOS).
3. Participants using GLP-1 receptor agonists (GLP-1 RA) for either diabetes or weight loss will not be eligible unless they have been using the GLP-1 RA at stable dose for ≥ 1 year and have not had any active weight loss ($< 10\%$ decrease in weight over past 6 months)
4. Use of any specific pharmacological treatments for NAFLD/NASH except vitamin E within the 3 months before screening visit.
5. Known cirrhosis, Child-Pugh score ≥ 7 , stage 4 fibrosis on biopsy, or clinical evidence of cirrhosis or portal hypertension on imaging or exam. If a subject is not known to be cirrhotic at screen but is found to be cirrhotic based on the results of liver biopsy at baseline, this subject will be referred to a hepatologist for clinical care and will be excluded from further participation in the study.

6. Chronic systemic corticosteroid use in the ≤6 months prior to the baseline visit. This includes physiologic steroid treatment in patients with adrenal insufficiency.
7. Chronic use of Actigall, methotrexate, amiodarone, tamoxifen, anticonvulsants, or cyclosporine
8. Known diagnosis of HIV-infection, alpha-1 antitrypsin deficiency, Wilson's disease, hemochromatosis, or autoimmune hepatitis
9. Use of GH or GHRH within the past 6 months
10. Change in lipid lowering or anti-hypertensive regimen within 2 months of screening
11. HgB < 10.0 g/dL or Creatinine >1.5mg/dL. If creatinine is above the upper limit of normal for the assay but <1.5mg/dL, then GFR must be >60mL/min for participant to be eligible.
12. Active malignancy
13. For men, history of prostate cancer or evidence of prostate malignancy by PSA > 5 ng/mL
14. Severe chronic illness judged by the investigator to present a contraindication to participation
15. History of hypopituitarism, head irradiation or any other condition known to affect the GH axis. Use of macimorelin.
16. Use of physiologic testosterone (men) or estrogen or progesterone (women) unless stable use for a year or more prior to study entry
17. Routine MRI exclusion criteria such as the presence of a pacemaker or cerebral aneurysm clip
18. Weight loss surgery within 1 year before baseline. Weight loss surgery more than 1 year prior to baseline visit is permissible as long as no active weight loss (<10% decrease in weight over past 6 months)
19. For women, positive urine hCG, trying to achieve pregnancy, or breastfeeding
20. For women able to become pregnant, unwillingness to use an acceptable form of birth control during the study. Acceptable forms of birth control include: abstinence from heterosexual vaginal intercourse, tubal ligation, male partner vasectomy, intrauterine device, etonogestrel implant (Nexplanon), or simultaneous use of TWO of the following: (a) contraceptive patch, pills, or vaginal ring, (b) diaphragm, (c) condoms.
21. Known hypersensitivity to tesamorelin or mannitol
22. Not willing or able to adhere to dose schedules and required procedures per protocol
23. Judge by the investigator to be inappropriate for the study for other reasons not detailed above.
24. Exclusion criteria for undergoing Coronary Computed Tomography Angiography (CCTA) follow. These do not exclude individuals from participating in the study, only from undergoing the CCTA:
 - a. Significant radiation exposure, including any history of radiation therapy, or any of the following in the 12 months prior to randomization: a) more than 2 percutaneous coronary interventions; b) more than 2 myocardial perfusion studies; 3) more than 2 CT angiograms
 - b. Active consideration for a procedure or treatment that involves significant radiation exposure as defined above in the 12 months following randomization
 - c. Contraindication to receiving nitroglycerin

Sources of Subjects/Recruitment Methods

Subjects will be recruited primarily from [name] MGH NAFLD Cohort and from the MGH Liver Clinic. We will also reach out to physicians in other relevant practices, such as Weight Management Clinics and other clinics here and at other institutions to see if they may have interested patients. We will also use the Research Patient Data Registry to identify appropriate patients, and, when patients have consented, we will use the RODY system to contact potentially eligible participants. The study will also be advertised on the MGH Clinical Trials website and, depending on the pace of recruitment, ads may also be placed in the community, including potentially in newspapers and in electronic venues such as Facebook or Craigslist. One option for patients to pre-screen will be to fill out an online REDCap survey that asks preliminary questions to determine eligibility and asks patients if they are willing to be contacted. A link to this survey will be included in any ads that are placed electronically.

III. Subject Enrollment

Methods of Enrollment

The study will be recruited primarily from the MGH NAFLD Cohort, with which [name] is involved, and the MGH Fatty Liver Clinic, in which [name] practices. In addition, the study will be advertised through other ambulatory clinics affiliated with the Massachusetts General Hospital, and we may contact physicians at relevant clinical practices (i.e., other liver clinics in the Boston area) to inform them about the study. We will also aim to recruit through the MGH Research Study Volunteer Participant database and Partners Clinical Trials website. Depending on the pace of recruitment, we may also choose to advertise through flyers and newspaper advertisements, Craigslist, and targeted advertisements on Facebook. Ads placed electronically, including in Craigslist and Facebook, will have a link to a REDCap Survey that will collect minimal information necessary to see if subjects would potentially be eligible, as well as contact information so that we can call them if they are potentially eligible. We may also perform a Partners Research Patient Data Registry (RPDR) search and/or an Epic Reporting Workbench search to identify patients who may be eligible. We will apply filters specific to our eligibility criteria, including age, BMI, NAFLD or fatty liver diagnosis. We will apply filters to exclude those who have 'opted out', and people with diabetes, malignancies, or prohibited medications listed. We may subsequently review the resulted medical records to hone in on those that meet our inclusion/exclusion criteria.. We will then send letters to potential participants through patient gateway and/or mail. We will also use Patient Gateway Targeted Research Announcements. Interested subjects will be directed to our rally website for more information and can call to speak with study staff.

Preliminary eligibility will be determined based on study staff interviews of interested subjects over the phone. Eligible subjects will then be scheduled for a screening visit. Potential participants who express interest in receiving study related materials and communications by e-mail (including a copy of the consent form) will be educated regarding the Partners HealthCare e-mail security policy. If the subject does not want to use encrypted email, they can consent to receive unencrypted e-mail, and this will be documented in the subject's record as per the subject's request.

Informed Consent

Written informed consent will be obtained by a licensed physician or NP prior to screening evaluation and testing. In all cases a licensed physician investigator will be available during the informed consent process in order to answer any further questions. When a study NP obtains consent, the NP will ask the participant if they would like to speak with a study physician about anything before signing the consent. Physician back-up will be available, usually in person and at minimum by telephone call during every consent visit performed by an NP. If the physician is only available by telephone and the participant wishes to have a video or in person conversation before signing, another time will be scheduled for this so the participant can speak with the physician before signing. Subjects will be informed that they may withdraw from participation in the study at any point. Subjects will be given a copy of the signed informed consent form.

For re-consenting purposes only, if there are changes to the consent form after a subject has initially provided consent, the subject may be called in advance of the study visit by a physician who will discuss any changes to the consent form with the subject over the phone. Provided the subject is in agreement with the changes to the consent form and has given verbal consent, the physician will then sign and date the updated consent form and document the telephone conversation (stating that the subject provided verbal consent over the phone regarding the changes in the consent form). When the subject returns for his/her next study visit, he/she will be given the consent form (signed by the physician during the aforementioned phone discussion) to sign. The subject will then be offered a copy of the signed consent form and the original will be filed in the research file.

Randomization

After signing consent and, prior to the baseline visit, eligible subjects will be randomized 1:1 to receive GHRH 1.4mg F4 formulation daily vs. identical placebo for 12 months (which will be followed by an open-label phase of 6 months). Randomization will be stratified by sex and vitamin E use ≥ 400 IU daily. A randomization list will be prepared by [name], the study statistician, using a permuted block algorithm with randomly varying block sizes. The randomization list will be provided to the MGH Research Pharmacy. Treatment assignment will be blinded to investigators, study staff, and subjects.

IV. Study Procedures

This study will include a 12-month, double-blind, randomized, placebo-controlled treatment period followed by a 6-month open label period during which all patients receive GHRH.

After the screen visit, there are 11 more study assessments, at baseline, 2wk, 1mo, 2mo, 3mo, 6mo, 9mo, 12mo, 12.5mo, 15mo, and 18 months. The baseline and 12 month assessments may require visits on 2-3 different days depending on subject availability and logistics.

The study schema is shown in the figure.

All study visits will occur at the MGH unless extenuating circumstances

require that safety visits be done remotely. Urine HCG will be performed at every visit for female subjects of child-bearing potential, except at baseline, at which a stat serum HCG will be performed (since a subset of women will also be undergoing coronary CT angiography at this visit).

Lifestyle and nutrition counseling

[figure not shown]
All subjects will be counseled in standard lifestyle modification at the baseline, 6, 12 and 18 month visits using standard recommendations for reduced dietary saturated fat (< 7%) and cholesterol intake (< 300 mg/day), and 150 minutes of activity equivalent to brisk walking a week (90, 91).

Remote Visits

In order to accommodate patient preferences, safety visits may be performed remotely if the participant is willing to go to a local Quest lab for the required lab testing using our study account and then have a phone call or video conference call with the investigator. This may only be done at the investigator's discretion and only for safety visits, NOT for the screening visit, the baseline visit, or the 12 month visit. If the visit is performed remotely the investigator will go through the CRF with the patient on the telephone or via a video visit and ask questions regarding any swelling of the hands or feet or any problems at the injection site (bruising, redness, etc.) If the patient describes physical signs that need to be seen by the investigator, the patient will be asked to come for a visit. So that a physical examination may be performed at a reasonable interval to assess for side effects, an in-person visit must be performed at least once during the first 3 months of the study (not counting the baseline visit), and at least once for the 12.5 month OR 15 month visit. The 6 month visit is typically performed in person because of the MRI and would only be offered remotely if a participant was not having an MRI at the 6 month visit for some independent reason (which would be documented as a protocol deviation). If a participant is not having MRI at 6 months, that visit may be conducted remotely. If a remote visit is performed for a safety visit at which drug is ordinarily dispensed, drug and supplies may be shipped to the participant via FedEx or UPS with signature required upon delivery. Drug will be checked to ensure identifiers match intended patient by at least 2 study staff, including at least one physician, before shipping.

Remote Consenting Visit (optional)

If there are circumstances such that a participant prefers remote consenting, we will offer a remote consenting visit as part of the screening visit. The patient will be (e)mailed a copy of the consent form prior to the visit. A study physician or NP will schedule a telephone call or video conference call to obtain informed consent, medical history, medication list, and drinking assessment. The consent will be obtained using RedCap e-consent. After consent, the patient will be allowed the option to obtain fasting labs at a local Quest site. Then, remainder of screening procedures, including bloodwork if not done previously, physical examination by study doctor, and procedures described below, will be done at MGH on a subsequent day.

Screen Visit (to determine eligibility)

1. Informed consent
2. Detailed H&P and medications (past and current), Lifetime Drinking History assessment
3. Fasting blood: AST, ALT, GGT, creatinine, albumin, total bilirubin, direct bilirubin, alkaline phosphatase, PT/INR and PTT, CBC, glucose, HbA1c, Hepatitis B sAg, Hepatitis C antibody, PSA (male subjects).
4. ^1H -MRS/MRI of abdomen for quantification of liver fat and to exclude abnormal liver lesions. This scan will also be used to assess VAT for those eligible subjects participating in the baseline visit.
5. Height and weight
6. Liver ultrasound ("Sonosite") may be performed if subjects do not have a diagnosis NAFLD or have had significant changes in health since NAFLD diagnosis. This is an optional procedure intended to provide an easier alternative to MRI for determining if a study candidate has fatty liver. Subjects may opt to have this test, and then could forego MRI and/or blood sampling if they do not have fatty liver.

Baseline Visit

The following procedures will be performed. Depending on availability of appointments for the various procedures as well as subject availability, subjects may be asked to come on 2-3 different days in order to complete all procedures. (For example, the liver biopsy will usually be performed on a different day than other procedures.)

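### Exclusion criterion 1 gives the heavy-alcohol limit in grams for women and in milligrams for men, so the men's limit as written is about 1/667 of the women's

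*Combined protocol and SAP*

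**What the plan says.** The alcohol criterion is item 1 of the exclusion list in section II of the combined protocol and SAP. It opens "Heavy alcohol use defined as consumption of" and then gives one limit per sex:

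- women: "> 20\text{g}$ daily for women"
- men: "> 30\text{mg}$ daily for men"

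One duration and look-back period closes the definition, "daily for men for at least 3 consecutive months over the past 5 years", and one instrument serves both sexes: "assessed using the Lifetime Drinking History Questionnaire". The sentence carries one pair of citations, references 25 and 89.

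In section IV, the Screen Visit list shows where the criterion is applied: "Detailed H&P and medications (past and current), Lifetime Drinking History assessment". The optional remote consenting visit also mentions a drinking assessment. Neither place gives a limit or a unit, and no other section restates the threshold.

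**The concern.** Everything in the sentence is shared by the two sexes except the number and the unit. A modest difference between 20 and 30 could be a deliberate sex-specific limit. A change from grams to milligrams has no stated reason, and it puts the men's limit far below anything that could be called heavy use.

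This is operative text. The criterion is applied to every man screened, and it is the only alcohol criterion in the eligibility list of a trial in non-alcoholic fatty liver disease. Followed literally, it would turn away men at trivial intake while admitting women who drink up to 20 g per day. If screening staff read another unit into it, the rule they apply is not the rule on the page, and a check of source records against the protocol would have to settle which of the two governs.

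**Working it through.** The plan derives no figure here, so there is nothing to reproduce. The check is a unit conversion.

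**Inputs from exclusion criterion 1**

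- Women's limit: 20 g per day
- Men's limit as written: 30 mg per day
- Minimum duration: 3 consecutive months, taken as about 90 days

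**Assumption not in the documents**

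- One drink contains 10 to 14 g of alcohol

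**Step 1. Common unit.** 1 g = 1000 mg, so the women's limit is 20 × 1000 = 20,000 mg per day and the men's is 30 / 1000 = 0.03 g per day.

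**Step 2. Gap between the limits as written.** Women to men: 20,000 / 30 = 667. Men to women: 30 / 20,000 = 0.0015.

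**Step 3. Part due to the unit alone.** If both numbers carried the same unit, men to women would be 30 / 20 = 1.5. The unit changes that ratio by 1.5 / 0.0015 = 1000. So 1000 is the unit factor and 667 is the gap between the two limits as they stand; they differ because the numbers 20 and 30 also differ.

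**Step 4. What the men's limit means over the criterion's own period.** There are two ways to read a daily limit held for three months.

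- *Averaged over the period.* 0.03 g × 90 days = 2.7 g in total. At 10 to 14 g per drink this is 2.7 / 14 = 0.19 to 2.7 / 10 = 0.27 of a drink. A single drink in the period averages 10 / 90 = 0.11 to 14 / 90 = 0.16 g per day, already above 0.03 g. The same sum for women is 20 × 90 = 1800 g, or 1800 / 14 = 129 to 1800 / 10 = 180 drinks.
- *Exceeded on each day.* Only men who drink every day for three months are caught, but at any amount above 0.03 g per day. Occasional or weekend drinkers are not caught.

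The first reading excludes a man for one drink in three months. The second excludes a man for a trivial amount taken daily. Neither matches a definition of heavy use.

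**The case against.** The strongest reply is that this is a self-evident typing slip. The item is labelled as heavy use, cites sources for its definition and gives grams for women in the same clause, so literal application is unlikely. That is probably right, and it is why the severity is low. It does not remove the point: an eligibility threshold has to be correct in the governing text, and the document nowhere confirms the men's limit that was intended.

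A second reply is that the text was read from PDF and the unit may have been misread. This cannot be fully excluded. However, both units are rendered cleanly in the same sentence, and the milligram unit in the next criterion, for fasting glucose, is intact.

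A third reply is that nothing in the inference depends on this. That stands. Eligibility is to be settled before treatment is assigned, and randomization is stratified by sex, so a fault in the men's criterion falls on both arms alike.

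Several stronger readings are tempting, and the documents do not support them:

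- *The limits differ 1000-fold between the sexes.* They differ about 667-fold; 1000 is only the factor between the units.
- *Almost every man who drinks at all is excluded.* That requires averaging over the period. On the day-by-day reading, occasional drinkers remain eligible.
- *A drink about once a year is enough.* Spreading 10 to 14 g at 0.03 g per day takes 333 to 467 days, but the criterion works over three consecutive months, so that span is not the relevant one.
- *Men were enrolled under an unwritten rule, or eligibility cannot be audited.* The screening form is not in the documents, and the questionnaire answers would be source data. Either statement would be conjecture.

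**Conclusion.** Wrong as written, minor severity. Two units in one sentence put the men's alcohol limit at 0.03 g per day, about 1/667 of the women's, and the literal rule would exclude men with almost any regular drinking. The conversion is exact. The comparison with drinks rests on the assumed 10 to 14 g per drink and on about 90 days for three months; no plausible change in either would alter the conclusion.

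The consequence is confined to which men are eligible and how that is documented. A reader might infer that the trial's result is compromised; sample size, power and the between-arm comparison are unaffected. A reader might also infer the intended men's limit by simply changing the unit. That is plausible, but the document does not state it, so the sponsor has to confirm it from the cited definition.

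**What to change.** Restate exclusion criterion 1 with both limits in one unit, after checking the sentence against the definition it cites and against the form used at screening. Then go through the screening records of men already assessed and confirm that the intended limit was applied; note any man whose eligibility would change.

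The cost is a one-word correction to the protocol and a review of the screening log. No analysis, sample-size or data-collection change is needed.
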